1.1 Background

Varicella-zoster virus (VZV) causes two clinically distinct diseases. Primary infection with VZV results in varicella, which is characterized by generalized conditions and widely scattered rashes and small blisters. In general, it occurs in infants or primary school-age children. After initial varicella infection in infant and young child recovers, the virus establishes latency in the spinal ganglia and other parts of the body. When latent VZV is reactivated, herpes zoster (HZ) occurs, usually manifested as local rash or blisters, accompanied by severe pain.

Typical HZ presents with rash and blisters, usually lasting for 2 to 4 weeks. It is often accompanied by intense pain being described as burning, stabbing pain. In some patients, even gentle touching may cause severe pain in the affected area, which is often referred to as allodynia. The HZ-related pain may be severe, with or without itching, and sometimes is too severe to tolerate.

The most common complication of HZ is post-herpetic neuralgia (PHN). PHN is the pain that persists after the rash/blister resolves. Affected patients often report persistent burning, throbbing, intermittent intense or shock-like pain, or indescribable allodynia. Age is the main risk factor for PHN. PHN may last for several months, and approximately 70% to 80% will resolve within 1 year, despite some may torture patients for many years [Dworkin, 2007]. Other risk factors may include severe HZ rash, which may be a precursor of PHN.

Other complications of HZ include disorders of the eyes, nerves, skin, and viscera, which can lead to severe disabilities. The most common ocular complications of HZ are keratitis and uveitis. Other ophthalmologic complications include ptosis, scleritis, retinitis, secondary glaucoma, and cataracts [Schmader, 2008; Carter, 2008]. Neurological complications of HZ include myelitis, motor neuropathy, brain, and spinal cord ischemic infarction, aneurysms, subarachnoid hemorrhage, and intracerebral hemorrhage [Gilden, 2009; Schmader, 2008].

The seroprevalence of VZV-IgG exceeds 90% in most adult populations, therefore, substantial individuals are at risk of developing HZ. Age is considered as the most common risk factor for shingles, and the incidence is relatively stable until the age of 40 years, with 2-3 in 1000 per year, and then gradually increases with age, with 5 in 1000 per year at the age of 50-59, and 10 in 1000 per year at ≥ 60 years [CDC, 2008; Oxman, 2005]. Although most data on the incidence of shingles comes from the United States (the Americas) and Europe, the available data indicate that the incidence of shingles is similar in other parts of the world (including Japan, South Korea, Australia and Latin America, mainland China).

About more than half of HZ cases occur in adults over 60, and >85 elders have a 50% chance of having shingles in their lives [Oxman, 2005]. Older patients also have the

highest risk of developing PHN, with those aged 70 years and older representing 18–50% of PHN [Oxman, 2005; Scott, 2006]. Patients with impaired cell-mediated immunity (CMI) due to disease, medication, medical intervention, or advanced age are at increased risk for HZ [Cohen, 2007].

Individuals who have received the attenuated VZV strain (OKA strain) vaccine or who have acquired protective immunity after natural VZV infection. VZV-specific antibodies (Abs) help control viral spread in immunocompromised individuals, potentially contributing to limiting the severity of herpes zoster (HZ). Additionally, in the efficacy study of Zostavax™, a correlation was observed between the concentration of anti-VZV antibodies generated after vaccination and protection against HZ [Levin, 2008]. The Oka strain live attenuated vaccine was approved by the U.S. FDA in 1995, followed by approval from regulatory bodies such as the National Medical Products Administration of China and the European Union for pediatric vaccination to prevent wild-type varicella infection in children. The high-dose OKA strain live attenuated vaccine, Zostavax™ (19,400 PFU/dose), was first approved by the U.S. FDA in 2006 for the prevention of herpes zoster in individuals aged 60 and above. In 2011, the indication was expanded to include those aged 50 and above. A single dose (0.65 mL, 19,400 PFU/dose) is administered subcutaneously in the deltoid region of the upper arm. Occasional adverse reactions, such as headache and local injection site reactions, may occur. Large-scale, multicenter clinical trials have verified that vaccination reduced the incidence of herpes zoster by 69.8% in immunocompetent individuals aged 50–59. This product was discontinued in the U.S. market in November 2020.

Shingrix™ is a recombinant subunit zoster vaccine developed by GlaxoSmithKline Biologicals (GSK Biologicals), which consists of VZV glycoprotein E (gE) and a special adjuvant. VZV gE was selected as the subunit vaccine antigen because gE is the target of the host immune response [Cohen, 2007]. gE plays an important role in viral infection and is the antigen to induce neutralizing antibodies against VZV. The vaccine does not contain live virus and has been shown to be safe in all populations, including immunocompromised population. The adjuvant system AS01B, used in combination with the VZV gE antigen (molecular weight approximately 70 KDa), was developed by GSK Biologicals. It is an oily adjuvant composed of the immunostimulant MPL (3-O-deacyl-4'-monophosphoryl lipid A), QS21, liposomes, etc. MPL is chemically detoxified LPA derived from Gram-negative bacteria *Salmonella Minnesota*. QS-21 is a saponin molecule (triterpene glycoside) extracted and purified from the bark of *Quillaja saponaria Molina*. It also contains phosphatidylcholine and cholesterol. Vaccines with this oil-based adjuvant can produce high-titer specific antibodies after vaccination, but the incidence of local side effects is much higher than other vaccines, and local pain may last for 2 to 3 weeks.

Shingrix™ in immunocompetent adults \geq 50 years reduced the incidence of herpes zoster and PHN by 97.2% and 91.2%, respectively, and by 89.8% and 88.8% in elders \geq 80 years [Cohen, 2007].

70 years, which showed better efficacy than live attenuated vaccine ZostavaxTM. However, the ultra-high incidence of side effects limits its promising application. In August 2020, this vaccine was officially launched in mainland China for the prevention of herpes zoster in individuals aged 50 and older. The vaccine is administered in a 50 μ g dose via intramuscular injection into the deltoid muscle, with two doses given 1 to 6 months apart.

Currently, there are two types of zoster vaccines available on the market in China. One is the imported ShingrixTM, and the other is the domestically produced live attenuated varicella-zoster virus vaccine, Ganwei[®], developed by Changchun BCHT Biotechnology Co., Ltd., which was approved for sale on January 31, 2023. Ganwei[®] is approved for adults aged 40 and older and requires only a single dose. Given the increasing incidence of herpes zoster among younger individuals, the rising morbidity rate, the large potential patient population in China, and the limited availability of zoster vaccines, the launch and application of zoster vaccines have become even more urgent.

The recombinant zoster vaccine (code: LZ901 vaccine) used in this clinical study is developed by Beijing Luzhu Biotechnology Co., Ltd. The active ingredient is varicella-zoster virus glycoprotein E Fc fusion protein expressed in CHO cells by gene recombination technology. The cloning and screening process of the LZ901 cell line has been carried out in chemically defined media without serum or other animal-derived components, any source of contamination with adventitious agents. The cryopreservation media used in the establishment of cell banks at all levels does not contain any blood or animal-derived proteins or protein hydrolysates. The culture medium and feed liquid used in the cell culture process are chemically defined. After the purification process of affinity chromatography, formaldehyde inactivation, anion exchange, molecular sieve chromatography, and others, the purified product is added with vaccine-specific stabilizer free of protein and proteolytic solution. After filtration through 0.2-micron sterilizing filter membrane, the resulting LZ901 bulk is appropriately diluted and adsorbed to aluminum hydroxide adjuvant to formulate a recombinant zoster vaccine. Each vial contains 0.5 ml, with a single human dose of 0.5 ml, containing 100 μ g of LZ901 protein. The residual DNA content in each dose of the vaccine is less than 1 pg (the Pharmacopoeia of China specifies a maximum of 100 pg), ensuring the safety of the vaccine to the greatest extent possible. This vaccine is primarily used for the prevention of herpes zoster and its complications caused by the varicella-zoster virus.

The LZ901 vaccine is a tetramer of varicella-zoster virus glycoprotein E (gE) and Fc fusion protein with a molecular weight of approximately 400 KDa. It is rich in O-glycosylation and N-glycosylation, with glycosylation types covering those have been detected in VZV infection in humans. The LZ901 molecule contains a structure that actively presents VZV gE to Fc γ receptors (Fc γ R) on the surfaces of dendritic cells and monocytes. This receptor-mediated endocytosis efficiently initiates an immune response

against VZV gE, generating high-titer antibodies and a robust cellular immune response. The results of Phase I and Phase II clinical trials (see data in section 4.2.3) show that the recombinant zoster vaccine is safe and well-tolerated in healthy individuals aged 50-70 years when administered with a 0 and 30-day immunization schedule via intramuscular injection into the deltoid muscle. Adverse reactions are limited to common vaccine-related side effects, with a lower incidence than the active control vaccine (ShingrixTM). After full immunization, both anti-gE antibodies and anti-VZV antibodies were found to be at high levels, with a 100% seroconversion rate. Immunogenicity results were significantly superior to those of the placebo group, with the high-dose group showing more pronounced effects. In conclusion, the recombinant zoster vaccine is safe, well-tolerated, and immunogenic. The immunization schedule for this study is as follows: Experimental group: 100 µg/0.5 mL/dose of recombinant shingles vaccine, administered on days 0 and 30 (2 doses in total). Control group: 50 µg/0.5 mL/dose of recombinant shingles vaccine, administered on days 0 and 60 (2 doses in total).

1.2 Benefits and Risks

1.2.1 Benefits

Subjects may potentially benefit from receiving the study vaccine, specifically in preventing herpes zoster caused by VZV (Varicella Zoster Virus) infection.

Vaccination against herpes zoster is the most effective method of prevention, and currently, only two zoster vaccines are available on the market in China. The development and launch of our recombinant zoster vaccine holds significant social value and benefit for China large potential patient population. It will greatly alleviate the pressure caused by the severe shortage of zoster vaccines in the country, addressing the demand for zoster vaccines in China and contributing to the improvement of public health.

1.2.2 Risks

LZ901 Phase I clinical trial (40 subjects with study vaccine) risk summary: After receiving the experimental vaccine (both high and low doses), the occurrence of local and systemic adverse events was as follows: pain (13 cases), fatigue (4 cases), headache (4 cases), abdominal pain (2 cases), swelling (2 cases), pruritus (2 cases at the injection site), erythema (1 case), chills (1 case), myalgia (1 case), pharyngeal discomfort (1 case), maculopapular rash (1 case), pruritus (1 case at another site), and pruritic rash (1 case). These were mostly grade 1 adverse events (AEs), which resolved on their own without the need for treatment, and no grade 3 or higher AEs were observed.

Phase II clinical trial (300 subjects with study vaccine) risk summary: After receiving the experimental vaccine (both high and low doses), the occurrence of local and systemic adverse events was as follows: pain (41 cases), induration (5 cases), swelling (3 cases), erythema (9 cases), pruritus (12 cases), fatigue (18 cases), and headache (6 cases).

cases). In the high-dose group (100 µg/dose), the most common adverse event was pain at the injection site (17.45%). The severity of adverse events was as follows: grade 1 (26.85%), grade 2 (6.04%), and grade 3 (2.01%). These adverse events did not require treatment and resolved on their own. Overall, the safety of the vaccine was favorable.

Known Risks: Based on the results of Phase I and Phase II clinical trial and previous vaccine experience, intramuscular injection is an invasive procedure. Subjects may experience local adverse reactions at the injection site, such as pain, swelling, induration, erythema, and pruritus, as well as systemic reactions like fatigue, headache, fever, gastrointestinal discomfort (nausea, vomiting, diarrhea, abdominal pain), and, in rare cases, allergic reactions. Most of these adverse events are mild, do not require treatment, and resolve on their own.

Potential Risks: The LZ901 vaccine is a recombinant protein expressed in CHO cells, which may contain trace amounts of residual CHO cell proteins. This could potentially cause allergic reactions in a small number of individuals who have previously received the CHO cell-derived hepatitis B vaccine. The vaccine contains excipients such as polysorbate and aluminum hydroxide adjuvant, which may cause mild irritation to the muscles at the injection site, leading to slight pain. A few individuals may not achieve adequate immune protection and could still be at risk of contracting herpes zoster.

1.2.3 Summary of benefits and risks

This product is the first recombinant zoster vaccine in China to enter Phase III clinical trial, and the results of this study may support the vaccine approval for market release to meet the demand for zoster vaccines.

Subjects may gain immunity against related diseases through vaccination with the study vaccine, thereby preventing the occurrence of herpes zoster. Throughout the study, all subjects will receive the attention of the investigator. If any subject experiences intolerable adverse reactions, the investigator will promptly stop subsequent vaccinations or terminate the study and provide the necessary medical treatment until the event resolves, with full support from the sponsor.

The sponsor will closely monitor the risks of the study, maintain ongoing discussions with investigators about any adverse events occurring during the study, and promptly inform both investigators and subjects about the latest information regarding the experimental vaccine or similar vaccines. If any risks that may harm the subjects interests are identified, the study will be immediately suspended or terminated, and the relevant regulatory authorities will be notified.

2. Study objectives and endpoints

2.1 Study Objectives

2.1.1 Primary objective

To evaluate the immunogenicity of cellular immune response induced by recombinant zoster vaccine (CHO cell) in subjects aged 50 years and older, in comparison to the control vaccine.

2.1.2 Secondary objective

To evaluate the immunogenicity and safety of humoral immune responses induced by recombinant zoster vaccine (CHO cells) in subjects aged 50 years and older.

2.2 Study Endpoints

2.2.1 Primary endpoints

The proportion of specific CD4+/CD8+ T cells activating at least two cytokines (TNF- α , IFN- γ , IL-2, CD40L) 30 days after full immunization.

2.2.2 Secondary endpoints

Immunogenicity endpoints

- 1) Geometric Mean Concentration (GMC) and seroconversion rate of anti-gE antibodies 30 days after full immunization;
- 2) Geometric Mean Fold Increase (GMFI) in anti-gE antibodies 30 days after full immunization compared to baseline (Day 0).

Safety endpoints

1. Incidence of solicited adverse events (AE) within 0-7 days after each dose, including local (injection site) and systemic (non-injection site) reactions;
2. Incidence of unsolicited AEs within 0-30 days after each dose;
3. Incidence of AEs within 30 minutes after each dose;
4. Incidence of adverse events of special interest (AESIs) from the first dose through 30 days after full immunization;
5. Incidence of serious adverse events (SAEs) from the first dose through 6 months after full immunization.

3. Study design

3.1 Overall Design

The experimental group will receive two doses of the recombinant zoster vaccine (CHO cells) with an immunization schedule of 0 and 30 days. The control group will receive two doses of the Recombinant Zoster Vaccine (RZV, ShingrixTM) with an immunization schedule of 0 and 60 days.

The number of subjects in each group is shown in the table below:

Table 3 Treatment Groups

Age	Experimental group	Control group	Total target enrollment
50 and older	150	150	300

3.1.1 Sample Collection

3.1.1.1 Blood sample collection

Blood samples will be collected from all subjects once before vaccination and once 30 days after full immunization, for a total of two blood samples. The ELISA method will be used to measure varicella-zoster virus (VZV) gE-specific antibodies, and flow cytometry will be used to assess VZV gE-specific CD4+/CD8+ T cell activation. The proportion of subjects activating at least two cytokines (TNF- α , IFN- γ , IL-2, CD40L) will be calculated to evaluate the vaccine humoral and cellular immune response. Detailed blood sample collection time points, volumes, and purposes are shown in the table below:

Visit Time	Test items and blood collection volume (ml)		
	Serum Antibody	Cellular Immune	Total
D0	4.0-5.0	15.0-20.0	19.0-25.0
30 days after full immunization	4.0-5.0	15.0-20.0	19.0-25.0

Note: Serum antibody testing is performed using procoagulant tubes for blood collection; cellular immunity indicators are tested using anticoagulant tubes for blood collection.

3.1.1.2 Collection of Biological Samples for Suspected Herpes Zoster Cases

For all suspected herpes zoster cases, skin lesion samples should be collected whenever possible and tested by qPCR. Methods for biological sample collection (any of the following three methods may be chosen):

a) Polyester Swab Method: Use a sterilized needle to puncture the vesicle, then vigorously rub the base of the ruptured blister with a sterile polyester swab to collect infected epithelial cells. Place the swab directly into a sample tube containing virus preservation solution.

b) Glass Slide Method: Use the edge of a glass slide to scrape the selected maculopapules, ensuring that the slide collects infected epithelial cells. Then, using the same sterile polyester swab, wipe the base of the ruptured lesion and further wipe the edge of the glass slide to obtain infected epithelial cells. Place the swab into a sample tube containing virus preservation solution.

c) Crust Method: Use a glass slide to scrape the crusts from the herpes lesions and place

the collected crust directly into a sample tube containing virus preservation solution.

3.1.1.3 Urine sample collection (pregnancy test)

Women of childbearing age (all women from menarche to menopause) should be tested with a urine pregnancy test before vaccination, which must be performed on the day of vaccination and before each dose. Urine samples do not need to be stored after testing.

3.1.2 Vaccination

The experimental group will receive two doses of the recombinant zoster vaccine (CHO cells) with an immunization schedule of 0 and 30 days. The control group will receive two doses of the Recombinant zoster vaccine (RZV, ShingrixTM) with an immunization schedule of 0 and 60 days.

3.1.3 Follow-up visit

3.1.3.1 Immunogenicity observation

Blood samples will be collected from all subjects once before vaccination and once 30 days after full immunization, for a total of two blood samples. The ELISA method will be used to measure varicella-zoster virus (VZV) gE-specific antibodies, and flow cytometry will be used to assess VZV gE-specific CD4+/CD8+ T cell activation. The proportion of subjects activating at least two cytokines (TNF- α , IFN- γ , IL-2, CD40L) will be calculated to evaluate the vaccine humoral and cellular immune response.

3.1.3.2 Safety observation

Collect all AEs (adverse events) within 30 days after vaccination (including solicited AEs within 30 minutes, 0-7 days, and all unsolicited AEs within 0-30 days). Follow up on all SAEs (serious adverse events) and pregnancy-related events from the first dose of vaccination to 6 months after full immunization.

Solicited AEs include:

Injection site (local) AEs	Pain, pruritus, induration, swelling, rash, redness
Non-injection site (systemic) AEs	Fatigue, tiredness, fever, headache, insomnia, myalgia, skin and mucosal abnormalities, pain at non-injection sites, diarrhea, constipation, vomiting, nausea, acute allergic reactions, arthritis, arthralgia

Unsolicited AEs include: Any adverse event that is not a solicited AE or any solicited AE occurring outside the solicitation period (e.g., If the solicited AEs mentioned above occur more than 7 days after vaccination, they should be recorded as unsolicited AEs). Collection of AESIs (Adverse Events of Special Interest): Suspected cases of herpes zoster within 30 days following the first dose of vaccination to full immunization.

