Age	Experimental group	Control group	Total target enrollment																					
50 and older	150	150	300																					
Visit Time	Test items and blood collection volume (ml)																							
	Serum Antibody	Cellular Immune	Total																					
D0	4.0-5.0	15.0-20.0	19.0-25.0																					
30 days after full immunization	4.0-5.0	15.0-20.0	19.0-25.0																					

	
events from the first dose of vaccination to 6 months after full immunization.
 
Solicited AEs include:
 
 
 Injection site (local) AEs	Pain, pruritus, induration, swelling, rash, redness	
 
 Non-injection site (systemic) AEs	Fatigue, tiredness, fever, headache, insomnia, myalgia, skin and mucosal abnormalities, pain at non-injection sites, diarrhea, constipation, vomiting, nausea, acute allergic reactions, arthritis, arthralgia	
 
 
Unsolicited AEs include: Any adverse event that is not a solicited AE or any solicited AE occurring outside the solicitation period (e.g., If the solicited AEs mentioned above occur more than 7 days after vaccination, they should be recorded as unsolicited AEs).
 
Collection of AESIs (Adverse Events of Special Interest):
 
Suspected cases of herpes zoster within 30 days following the first dose of vaccination to full immunization.
	Injection site (local) AEs	Pain, pruritus, induration, swelling, rash, redness	Non-injection site (systemic) AEs	Fatigue, tiredness, fever, headache, insomnia, myalgia, skin and mucosal abnormalities, pain at non-injection sites, diarrhea, constipation, vomiting, nausea, acute allergic reactions, arthritis, arthralgia
Injection site (local) AEs	Pain, pruritus, induration, swelling, rash, redness				
Non-injection site (systemic) AEs	Fatigue, tiredness, fever, headache, insomnia, myalgia, skin and mucosal abnormalities, pain at non-injection sites, diarrhea, constipation, vomiting, nausea, acute allergic reactions, arthritis, arthralgia				
study vaccine	
Experimental Vaccine:
 
Vaccine Name: Recombinant zoster vaccine (CHO Cells)
 
Specification: 100μg/0.5ml/ vial
 
Lot Number: 20230201
 
Manufacturer: Luzhu Biopharmaceuticals (Zhuhai) Co., Ltd.
 
Control Vaccine:
 
Vaccine Name: Recombinant Zoster Vaccine (RZV, ShingrixTM)
 
Specification: 50 μg/0.5 ml/vial
 
Lot Numbers: 3472D, X4937
 
Manufacturer: GlaxoSmithKline Biologicals SA
				
Study Population					

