5.1.9.2 Follow-up Content

The safety observation content includes all adverse events (AEs) and serious adverse events (SAEs) that occur during the study, such as: pain, pruritus, induration, swelling, rash, redness, fatigue, tiredness, fever, headache, myalgia, etc. It also includes the occurrence of all SAEs and pregnancy events from the first dose of vaccination until six months after the full immunization schedule is completed.

Solicited AEs include:

Injection site (local) AEs	Pain, pruritus, induration, swelling, rash, redness
Non-injection site (systemic) AEs	Fatigue, tiredness, fever, headache, insomnia, myalgia, skin and mucosal abnormalities, pain at non-injection sites, diarrhea, constipation, vomiting, nausea, acute allergic reactions, arthritis, arthralgia

Unsolicited AEs include: Any adverse event that is not a solicited AE or any solicited AE occurring outside the solicitation period (e.g., If the solicited AEs mentioned above occur more than 7 days after vaccination, they should be recorded as unsolicited AEs).

Serious Adverse Events (SAEs)

This study will collect all SAEs occurring from the first dose of vaccination until six months after the completion of the full immunization schedule.

Pregnancy Events

All pregnancy events occurring from the first dose of vaccination until six months after the full immunization schedule will be collected. Details on pregnancy reporting, follow-up, and assessment are provided in Section 7.5.

Specially Monitored Adverse Events

Suspected cases of herpes zoster occurring from the first dose of vaccination until 30 days after the completion of the full immunization schedule will be collected.

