8.4.4 Safety

This study will primarily focus on the statistical analysis of treatment-emergent adverse events (TEAEs) occurring after vaccination. Adverse events occurring before vaccination will be listed separately. Unless otherwise specified, the term "adverse events" in the following sections refers to TEAEs.

Solicited adverse events occurring 0-7 days post-vaccination, as well as solicited adverse events related to vaccination, will be categorized and analyzed by group, type of reaction (systemic and local), and the severity of each solicited adverse event as listed in Section 3.1.3.2. For these events, the number of adverse events, the number of subjects experiencing them, and the incidence rate will be calculated.

The following adverse events will be categorized and analyzed by group, System Organ Class (SOC), and Preferred Term (PT), calculating the number of events, the number of affected subjects, and the incidence rate:

- Unsolicited adverse events occurring 0-30 days after each dose;
- Adverse events occurring within 30 minutes after each dose;
- All adverse events occurring 0-30 days after each dose;
- Adverse events of special interest occurring from the first dose to 30 days after full immunization;
- Serious adverse events occurring from the first dose to 6 months after full immunization.

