Acute Allergic Reaction**	Localized urticaria (water blisters), no systemic symptoms	Localized urticaria requiring treatment or mild angioedema not requiring treatment	Generalized urticaria or angioedema requiring treatment, or mild bronchospasm	Anaphylactic shock or life-threatening bronchospasm or laryngeal edema
Other				
Fatigue	No impact on daily activities	Affects normal daily activities	Severely affects daily activities, unable to work	Emergency visit or hospitalization
Pain at Non-Injection Sites# (Specify location at reporting)	Mild pain, no or minimal impact on daily life	Pain affects daily activities	Pain preventing daily activities	Disabling pain with loss of basic self-care ability

Notes:

FEV1% refers to the ratio of Forced Expiratory Volume in 1 second (FEV1) to Forced Vital Capacity (FVC).

* Changes in constipation and insomnia before and after vaccination should be monitored.

** Refers to Type I hypersensitivity reactions.

Refers to non-injection site pain other than myalgia, arthralgia, or headache.

For adverse events not covered in the grading tables above, refer first to the Guidelines for Grading Adverse Events in Preventive Vaccine Clinical Trials. If the guidelines do not provide criteria for evaluation, assess the severity according to the following standards.

Table 7 General Grading Criteria for Other Adverse Events

Grade 1	Grade 2	Grade 3	Grade 4	Grade 5
Mild: Short duration (<48h) or slight discomfort, no impact on activities, no treatment required.	Moderate: Moderate or mild impact on activities, may require minimal or no treatment.	Severe: Significant impact on activities, requires intervention, may require hospitalization.	Life-threatening: Potentially life-threatening, severe impact on activities, requires intensive treatment.	Death.

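### *Fatigue* and *tiredness* are two solicited entries with one grading row, so the per-term figures for the leading Phase II systemic reaction can be split or double-counted

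*Protocol*

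**What the plan says.** Section 3.1.3.2 lists the systemic solicited adverse events, starting "Fatigue, tiredness, fever, headache, insomnia, myalgia, skin and mucosal abnormalities, pain at non-injection sites". The synopsis repeats the list ("Fatigue, tiredness, fever, headache, insomnia, myalgia"). Section 5.1.9.2 repeats it in a table and again in running text: "pain, pruritus, induration, swelling, rash, redness, fatigue, tiredness, fever, headache, myalgia, etc". No section defines a difference between fatigue and tiredness or says that they are one item.

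Section 8.4.4 takes that list as the unit of analysis. Solicited events are broken down by group, by reaction type and by "the severity of each solicited adverse event as listed in Section 3.1.3.2", and for these events "the number of adverse events, the number of subjects experiencing them, and the incidence rate will be calculated".

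Table 6 in section 11.3 has a row for Fatigue, whose Grade 3 reads "Severely affects daily activities, unable to work". No row in Tables 4 to 6 names tiredness. A fallback follows: "For adverse events not covered in the grading tables above, refer first to the Guidelines for Grading Adverse Events in Preventive Vaccine Clinical Trials". Failing a criterion there, the general scale in Table 7 applies.

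Section 1.2.2 reports earlier experience under one term only. Its Phase II list includes "pruritus (12 cases), fatigue (18 cases", followed by 6 cases of headache.

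**The concern.** The two words are near-synonyms in ordinary use, and the protocol's own grading table and earlier trial summaries treat the symptom as one reaction. The solicited list makes it two. A subject with one episode could report it under either word, which divides the incidence between two rows, or under both, which counts one episode as two events.

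The incidence of solicited adverse events within 0-7 days of each dose is a named secondary safety endpoint (section 2.2.2). Sections 1.1 and 5.2 describe LZ901 as having fewer adverse reactions than the control vaccine, so readers are likely to compare the arms term by term. A split or duplicated row makes that comparison hard to read for the systemic reaction most often reported with LZ901 in Phase II. In absolute terms the distortion grows with the true rate, so it need not be equal in the two arms.

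**Working it through.** **Step 1: match the list to the grading rows.** Section 3.1.3.2 names 15 systemic terms.

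| Solicited systemic term | Named grading row |
|---|---|
| Fever | Table 5 |
| Fatigue, headache, insomnia, myalgia, skin and mucosal abnormalities, non-injection-site pain, diarrhea, constipation, vomiting, nausea, acute allergic reaction, arthritis, arthralgia (13 terms) | Table 6 |
| Tiredness | none |

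Fourteen of the 15 terms (1 + 13) have a named row. Tiredness is the only one without.

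**Step 2: follow the analysis rule.** Section 8.4.4 works from the events as listed in 3.1.3.2. Read literally, fatigue and tiredness each get their own counts of events and subjects and their own incidence. The solicited events are not tabulated by coded term in that paragraph. System Organ Class and Preferred Term are used for the other categories, one of which is all adverse events within 0-30 days.

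**Step 3: size, as an illustration.** The inputs are the Phase II counts in section 1.2.2 (18 fatigue, 6 headache, 300 LZ901 recipients, low and high dose pooled) and 150 subjects per arm from section 3.1. I assume one case per subject.

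- Fatigue: 18/300 = 6.0%. Headache: 6/300 = 2.0%. Pruritus has 12 cases with no site stated and is also below 18, so fatigue ranks first among systemic reactions either way.
- Expected in one arm of this trial at that rate: 0.06 × 150 = 9 subjects.
- All reports under one term: 9/150 = 6.0%.
- Even split: 4.5/150 = 3.0% on each row. Under other splits the Fatigue row can show anything from 0% to 6.0%.
- Every episode recorded under both terms: 2 × 9 = 18 events instead of 9.

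**Step 4: what does not move.** A subject counts once towards any systemic reaction, whichever word is used and however many rows are filled. The primary endpoint is a cellular immune response and does not use these data.

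**The case against.** **Splitting is permitted, not certain.** The Diary Card and eCRF are not shown. An investigator reviews the card at day 7 and could treat the two words as one. This stands: the figures can be distorted, but the protocol does not show that they will be.

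**It may be a translation doublet.** The text is visibly translated, and Table 4 itself joins related terms with a comma in one row (induration with swelling, erythema with redness). This is plausible and cannot be settled from the document. But where Table 4 shares a row it names both terms. The Fatigue row does not name tiredness, and whoever builds the card and database works from the list as written.

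**Coding may reunite the terms.** Section 10.2.9 requires MedDRA coding, and the table of all events within 0-30 days is by Preferred Term. If both words code to one term, which cannot be checked here, that table gives an unsplit subject count. It would then differ from the solicited table on the same data and would still count a doubly recorded episode twice.

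**The size is illustrative.** The Phase II figure pools two dose levels while this trial uses one, and the split and duplication patterns are assumed. This stands.

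**Two stronger readings are not supported.** A reader might infer that tiredness will be graded on a different scale from fatigue. If tiredness is simply fatigue, the Fatigue row covers it and the fallback is never reached. If it is not, the external guideline comes first, and its content is not at hand. What can be said is that tiredness has no named row.

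A reader might also infer that the choice of word changes the 15% suspension rule (section 6.5) or the postponement of the second dose (section 6.1.1). The clearest difference between the scales is admission to hospital: Grade 4 in the Fatigue row and possibly Grade 3 in Table 7. Both are Grade 3 or higher, so neither rule changes. The suspension rule counts subjects, so duplicate entries add nothing, and it also requires that events fail to fall below Grade 3 within 48 hours. The postponement rule concerns events on the day of vaccination, after the 7-day solicited period of the first dose has ended.

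**Conclusion.** The point holds as a minor defect in descriptive safety reporting. The protocol fixes the solicited list, the grading rows and the rule that links them, and on this symptom they do not match. The incidence and event count for the leading Phase II systemic reaction can therefore be divided between two rows or counted twice. On the Phase II rate, a true 6.0% could print as two rows of 3.0%, or 9 events as 18. These figures assume one case per subject, a rate carried over from pooled dose levels, and either an even split or universal double recording.

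Safety is a secondary objective with no hypothesis test, so no formal conclusion depends on this.

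**What to change.** Replace the two entries by one solicited term, *Fatigue (tiredness)*, in section 3.1.3.2, section 5.1.9.2, the synopsis, the Diary Card and the eCRF. State that it is graded by the existing Fatigue row of Table 6. Section 8.4.4 then needs no change beyond noting that one episode is one event.

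If cards with both words are already in use, combine the two terms at analysis: one event per episode, one count per subject and dose, taking the higher of the recorded grades. Fix this rule before database lock.

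The cost is a wording change, or a short derivation rule if data collection has begun. No new grading criterion is needed. If the sponsor does intend two distinct reactions, the alternative is to define the difference and give tiredness its own named row.
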